### 8.8.2 Permitted concomitant medication

- Steroids
  - Oral corticosteroids are permitted to be taken at the time of study entry at the dose of  $\leq 10$  mg prednisone or equivalent.
  - Intranasal or inhaled corticosteroids are authorized as needed throughout the study.
  - At any time the corticosteroid dose can be modified, temporarily or permanently discontinued, or a new steroid initiated (irrespective of the mode of administration), for any reason per investigator judgment including but not limited to worsening of RA, treatment of AEs or for the prevention of corticosteroid associated side effects.
- Nonsteroidal anti-inflammatory drugs and analgesics:
  - Non-steroidal inflammatory drugs (NSAIDs) and cyclo-oxygenase-2 inhibitors (COX-2) are permitted as needed throughout the study. The dose used should be in accordance with the approved dose in the country in which the study is conducted.
  - Narcotic or non-narcotic analgesics (with no anti-inflammatory properties) for RA pain relief are permitted based on investigator judgment that there is insufficient RA pain relief with stable maintenance NSAIDs. As limited treatment for inter-current pain, all analgesics (with no anti-inflammatory properties) are allowed. These analgesics, including acetaminophen, should be avoided within 6 hours of efficacy assessments, including physical function and quality of life assessments.
  - Acetaminophen use should be limited to 4g/24h. Specific attention should be paid to co-administration of hepatotoxic drugs (see specific [Section 10.2.4](#)).
- Cytochrome P450 enzyme substrates

IL6 has been shown to reduce CYP1A2, CYP2C9, CYP2C19 and CYP3A4 enzyme expression in in-vitro studies. Therefore, when IL-6 is blocked using sarilumab IL-6 levels “normalize” and CYP450 enzymes may increase which could result in dose adjustment for drugs that are metabolized by CYP450 enzymes. As a precautionary measure, drugs which are metabolized via these cytochromes and with a narrow therapeutic index should be adjusted if needed: dose to be increased to maintain efficacy after initiation of sarilumab and to be decreased after sarilumab is stopped. Some examples of CYP450 substrates with a narrow therapeutic index, requiring monitoring of effect are warfarin or monitoring of drug concentration include cyclosporine, theophylline, digoxin, antiepileptics, such as carbamazepine (Carbatrol®, Tegretol®), divalproex (Depakote®), phenytoin (Dilantin®), or valproic acid (Depakene®); or antiarrhythmics, such as disopyramide (Norpace®), procainamide (Procan®, Pronestyl®), or quinidine (Quinidex®, Quin-Release Quin-G®).
- Lipid lowering drugs:

Lipid lowering drugs are permitted. Anti-IL-6 drugs, including sarilumab are known to increase serum cholesterol levels and this effect will be closely monitored during the study. If, during the study, patients are found to have significant increase in cholesterol levels, then cholesterol lowering therapy per National Cholesterol Education program

(NCEP)Adult Treatment Panel (ATP)3 (NCEP/ATP3) or local guidelines should be initiated or the dose of concomitant lipid lowering drug(s) adjusted. A referral to a specialist should be considered when dyslipidemia is difficult to manage.

## 8.9 CONCOMITANT TREATMENT

A concomitant treatment is any treatment received by the patient, at the same time as the IMP(s), other than medications. Treatments received during the study should be recorded on the corresponding pages of the patient's e-CRF as appropriate.

Joint replacement is permitted during the study. The IMP should be temporarily interrupted prior to surgery as per applicable guidelines and the IMP restarted as soon as proper wound healing is established.

NOTE: The IMP can be temporarily discontinued for  $\leq 59$  days (3 IMP doses can be missed). If the re-initiation of the IMP occurs later than 38 days since the last IMP dose (2 IMP doses were already missed), the IMP has to be administered at the study site and the patient to be observed for 30 minutes for any medical events.

## 8.10 TREATMENT ACCOUNTABILITY AND COMPLIANCE

Measures taken to ensure and document treatment compliance and investigational medicinal product accountability include:

- Proper recording of medication treatment pack number on appropriate e-CRF page for accounting purposes.
- All medication treatment kits (containing vials, or prefilled syringes, whether empty or unused study medication) are returned by the patient at each visit.
  - As the used prefilled syringes cannot be safely returned to the study site after administration of IMP, the completed patient injection diary (returned to the site at each visit), returned treatment kit boxes and any unused prefilled syringes will be used for drug accountability purposes.
- The study coordinator tracks treatment accountability/compliance, either by diary, or by counting the number of empty IMP containers (vials or prefilled syringes), and fills in the appropriate page of the patient treatment log.
- The monitor in charge of the study then checks the data entered on the investigational medicinal product administration page by comparing them with the investigational medicinal product which has been retrieved and the patient treatment log form.

### **8.11 RETURN AND/OR DESTRUCTION OF TREATMENTS**

All partially used or unused treatments will be retrieved by the investigator. A detailed log of the returned IMP will be established with the Investigator (or the pharmacist) and countersigned by the Investigator and the Monitoring Team.

Used or unused kits can be destroyed at site level upon approval of the study sponsor.

## 9 ASSESSMENT OF INVESTIGATIONAL PRODUCT

### 9.1 ENDPOINTS

#### 9.1.1 Primary endpoint

Incidence of adverse events: (see [Section 10.1](#))

#### 9.1.2 Secondary endpoints

The secondary endpoints will be:

- The proportion of patients at week 12 and over time who achieve ACR20/ACR50/ACR70, DAS28 Remission, and EULAR Response.
- DAS28-CRP over time
- HAQ-DI results over time.
- Van der Heijde modified total Sharp score over time and incidence of radiographic progression of the van der Heijde modified total sharp score for the subset of patients who previously completed the study EFC11072 Part B.
- Each component of the ACR over time.
- Health economic endpoints and Patient reported outcomes: patients will continue in evaluation of the health economic endpoints as per the initial study.

##### 9.1.2.1 ACR20/ACR50/ACR70

Signs and symptoms are assessed with a composite rating scale of the ACR (American College of Rheumatology) that includes 7 variables:

- Tender Joints Count (TJC)
- Swollen Joints Count (SJC)
- Levels of an acute phase reactant (CRP level)
- Patient's assessment of pain
- Patient's global assessment of disease activity
- Physician's global assessment of disease activity
- Patient's assessment of physical function

The details of the ACR score are presented in [Appendix B](#).

ACR20 is defined as the percentage of patients who achieve at least 20% improvement in both tender joint count and swollen joint count and, at least 20% improvement in at least 3 of the 5 other assessments.

ACR50 is defined as the percentage of patients who achieve at least 50% improvement in both tender joint count and swollen joint count and, at least 50% improvement in at least 3 of the 5 other assessments.

ACR70 is defined as the percentage of patients who achieve at least 70% improvement in both tender joint count and swollen joint count and, at least 70% improvement in at least 3 of the 5 other assessments.

ACR scores will only be assessed up to Week 264 at the time points as per study flowchart.

### **9.1.2.2 DAS28-CRP**

Disease activity state will be measured and presented using the disease activity score (DAS28). In this protocol, unless otherwise specified, DAS28 refers to DAS28-CRP. DAS28 is a composite score that includes 4 variables:

- Tender Joints Count (based on 28 joints - see [Appendix B](#))
- Swollen Joints Count (based on 28 joints - see [Appendix B](#))
- General health assessment (GH) by the patient assessed from the ACR RA core set questionnaire (patient global assessment)
- Marker of inflammation assessed by the hs-CRP.

It is a continuous measure allowing for measurement of absolute change in disease burden and percentage improvement. It has been extensively validated for its use in clinical trials and accepted by Health Authorities. The DAS28 can be calculated using the following formula:

$$\text{DAS28} = 0.56 \times \sqrt{28TJC} + 0.28 \times \sqrt{28SJC} + 0.36 \times \text{Log}(\text{CRP}+1) + 0.014 \times \text{GH} + 0.96$$

The DAS28 provides a number indicating the current activity of the RA. A DAS28 above 5.1 means high disease activity, whereas a DAS28 below 3.2 indicates low disease activity and a DAS28 below 2.6 means disease remission.

### **9.1.2.3 EULAR response**

Improvement in disease activity will also be assessed using the EULAR response criteria:

- Good response = DAS28 improvement of >1.2 and a present DAS28 score  $\leq 3.2$
- Moderate response = DAS28 improvement of >0.6 to  $\leq 1.2$  and a present DAS28 score  $\leq 5.1$ , or an improvement >1.2 and a present score >3.2
- Nonresponse = DAS28 improvement of  $\leq 0.6$ , or an improvement >0.6 to  $\leq 1.2$  and a present DAS28 score >5.1

#### **9.1.2.4 Van der Heijde modified Total Sharp Score**

The van der Heijde modified Sharp method is a composite X-ray scoring system used to assess structural (joint) disease progression in RA (see [Appendix C](#)). The method evaluates both joint erosions (JE) and joint space narrowing (JSN) in bilateral hand and foot joints.

The change from baseline in van der Heijde modified total Sharp score will be evaluated for patients who completed the EFC11072 Part B study in order to demonstrate maintenance of sarilumab effect on joints. It will be assessed at week 48, 96, 144 and 192, or at the end of treatment for patients who prematurely discontinue from the study before Week 192.

NOTE: the sponsor will not perform any medical evaluation on collected X-rays. They will be blindly assessed by independent graders and modified Van Der Heijde Total Sharp Score will be calculated per patient per visit.

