### **13.2 ANALYSIS ENDPOINTS**

#### **13.2.1 Demographic and baseline characteristics**

Baseline for this study is defined to be the baseline measurement from the previous (initial) study.

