### **13.5.5 Analyses of efficacy endpoints**

There will be no confirmatory analysis for the efficacy variables. All analysis will be done descriptively on the safety population by visit in observed case, as appropriate.

For categorical variables, for example, percentage of patients who have maintained/reached ACR20 overtime, the number and percentage will be provided from all patients who have data available at that time point, and the 95% confidence intervals will be calculated if appropriate.

For continuous variables, descriptive statistics such as the mean, standard deviation, median, minimum and maximum will be provided. In addition, 95% confidence interval of the mean will be presented. This applies to the original values and change (or percent change) from baseline.

Change from baseline in the van der Heijde modified total Sharp scores (mTSS) will be summarized for patients from EFC11072 Part B only. Descriptive statistics, including the mean, standard deviation, median, minimum and maximum will be provided, along with 95% confidence intervals. The actual values will be similarly summarized.

Radiographic progression of the mTSS is defined as a change from baseline in the mTSS  $> 0$ . A change from baseline in the mTSS of less than or equal to zero is considered as no progression. The event of missing a change from baseline in the mTSS will be considered as progression. Summary of incidence of radiographic progression of mTSS will be provided.

Additional sensitivity analyses may be performed if necessary.

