#### **2.1.4 Efficacy endpoints**

Efficacy is a secondary endpoint of this study. The efficacy variables will include:

- ACR20 response over time up to Week 264
- ACR50 and ACR70 response over time up to Week 264
- Change from baseline in ACR components up to Week 264
- DAS28 –CRP response over time

- DAS28 remission over time
- EULAR response over time
- Change from baseline in the van der Heijde modified total Sharp score (for patients from EFC11072 Part B Cohort 2 and Cohort 1 selected dose arms with an end of treatment X-ray evaluation) at Weeks 48, 96, 144 and 192 or EOT if EOT is prior to Week 192
- Incidence of radiographic progression of the van der Heijde modified total sharp score at Weeks 48, 96, 144, and 192 or EOT if EOT is prior to Week 192
- Change from baseline in HAQ-DI over time up to Week 264.

Note that TJC and SJC (both based on 28 joints), patient's global assessment of disease activity and hs-CRP will still be assessed after Week 264 to calculate DAS28.

As mentioned before, the baseline value for efficacy parameters is the original baseline from the previous study databases for patients who rolled over to LTS11210.

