### *X-ray data reading*

#### Campaign 1

X-rays read in Campaign 1 will include baseline and EOT (or last available visit) from EFC11072, Week 48 and any unscheduled visits between Week 0 and Week 48 in LTS11210. Two primary readers and an adjudicator will perform reading of data up to Week 48 in LTS11210 (see details in [Appendix D](#)). The X-rays at baseline and Year 1 (EOT or last available visit in EFC11072) will be reread.

The linear extrapolation method will be used to impute missing modified total Sharp score, erosion score, or joint space narrowing score at Week 48 in LTS11210 from Campaign 1 data for patients who have EOT (or last available data) in EFC11072 and any unscheduled visit data between Week 0 and Week 48 in LTS11210. In the linear extrapolation method, for example, the missing modified total Sharp score at Week 48 is imputed according to the following formula:

$$\text{Week 48 modified total Sharp score} = \text{EOT score in EFC11072} + 336 * (\text{modified total Sharp score of the last measurement in LTS11210} - \text{EOT score in EFC11072}) / (\text{date of last measurement in LTS11210} - \text{date of EOT visit in EFC11072}).$$

### Campaign 2

X-rays in Campaign 2 will include baseline from EFC11072, Weeks 48 and 96, and any unscheduled visits between Week 48 and Week 96 in LTS11210. The linear extrapolation method will be used to impute missing the modified total Sharp score, erosion score, or joint space narrowing score at Week 96. Similarly, the missing modified total Sharp scores at Week 96 are imputed by the linear extrapolation method according to the following formula:

$$\text{Week 96 modified total Sharp score} = \text{Week 48 score} + 336 * (\text{modified total Sharp score of the last measurement} - \text{Week 48 score}) / (\text{date of last measurement} - \text{date of Week 48 measurement}),$$

### Campaign 3

X-rays in Campaign 3 will include baseline from EFC11072, Weeks 96, 144 and 192 (or EOT), and any unscheduled visits between Week 96 and Week 192 (or EOT) in LTS11210. The linear extrapolation method will be used to impute missing the modified total Sharp score, erosion score, or joint space narrowing score at Weeks 144 and 192 in LTS11210 based on Campaign 3 data. Similarly, the missing modified total Sharp scores at Week 144 and Week 192 in LTS11210 are imputed by the linear extrapolation method according to the following formula:

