#### **2.4.5 Analyses of efficacy endpoints**

There will be no confirmatory analysis for the efficacy variables. All analysis will be done descriptively on the safety population by visit in observed case, as appropriate. In addition to the by-visit analysis, efficacy assessments summarized on a yearly basis will be provided.

The baseline value for efficacy parameters is the original baseline from the previous studies. The value at Week 0 is the last non-missing measurement in data collected at scheduled visits: visit1, visit2, and/or visit1/2 in LTS11210 or EOT visit of previous studies prior to first IMP in LTS11210 study.

For categorical variables, for example, percentage of patients who have maintained/reached ACR20 overtime, the number and percentage will be provided from all patients who have data available at that time point, and the 95% confidence intervals (CI) will be calculated if appropriate.

For continuous variables, descriptive statistics such as the mean, standard deviation, median, minimum and maximum will be provided. In addition, 95% confidence interval of the mean will be presented. This applies to the original values and change (or percent change) from baseline.

The 2-year (EFC11072 52 weeks + LTS11210 48 weeks) X-ray data from Campaign 1 will be described using the van der Heijde modified total Sharp score for the subset of patients who previously completed study EFC11072, Part B when the 2-year X-ray data are available for all these patients. The modified total Sharp score and the change from baseline in the modified total sharp score will be described using mean, standard deviation, median, minimum and maximum, along with 95% confidence intervals. There is no formal treatment comparison and no alpha adjustment will be made (further analyses will be in the report of integrated summary of efficacy). In addition, the incidence of radiographic progression will be summarized using descriptive statistics.

The above analyses will also be performed for X-ray data from Campaign 2 and Campaign 3 respectively once X-ray data are available.

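### mTSS change and progression are counted from the EFC11072 baseline, so the progression rate cannot separate parent-study damage from progression during LTS11210; same-campaign interval results should be added

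*Protocol*

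**What the plan says.** Protocol 9.1.2.4 gives the X-ray endpoint a purpose: change from baseline is evaluated in those "who completed the EFC11072 Part B study in order to demonstrate maintenance of sarilumab effect on joints".

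Baseline is fixed in both documents. Protocol 13.2.1: "Baseline for this study is defined to be the baseline measurement from the previous (initial) study". SAP 2.1.4: "the baseline value for efficacy parameters is the original baseline from the previous study databases for patients who rolled over to LTS11210".

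Protocol 13.5.5 then states: "Radiographic progression of the mTSS is defined as a change from baseline in the mTSS" greater than zero, and counts a missing change as progression. SAP Appendix C repeats the missing-data rule after linear extrapolation of missing scores. SAP Appendix B lists change from baseline and the progression rate at all visits, and enters No for supportive, subgroup and other analyses of both.

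Actual scores are also reported. SAP 2.4.5: "The modified total Sharp score and the change from baseline in the modified total sharp score will be described", and the same analyses are repeated for each campaign. SAP 2.3.2 presents efficacy by previous treatment.

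On the films, SAP 2.1.4 H says "X-rays read in Campaign 1 will include baseline and EOT (or last available visit) from EFC11072, Week 48", and adds: "The X-rays at baseline and Year 1 (EOT or last available visit in EFC11072) will be reread". Campaign 2 lists the EFC11072 baseline and Weeks 48 and 96. Campaign 3 lists the EFC11072 baseline and Weeks 96, 144 and 192 (or EOT).

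**The concern.** Maintenance of effect is a question about what happens after patients enter the extension. A result cumulated from the parent-study baseline carries parent-study damage into every later visit. No change from LTS11210 entry, and no change over any interval within LTS11210, is specified as an outcome; slopes within the extension appear only in the extrapolation formulas.

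The binary endpoint is the most exposed, because one early rise marks the patient at all four extension time points unless the score later falls. The split by previous treatment has the same difficulty: differences that arose in EFC11072 reappear in each later table and could be read as differences during the extension. In former placebo patients the pre-entry window covers placebo and, for some, open-label sarilumab rescue, which SAP 1.1 allowed in Part B from Week 16.

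**Working it through.** The plan gives no target figure for this endpoint. The inputs are its definitions, its visit weeks and the 52-week duration of Part B.

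**1. Share of the change window that precedes entry.** Formula: 52/(52 + w), with w the LTS11210 week. At w = 48 the total of 100 weeks matches the make-up of the two-year data in SAP 2.4.5.

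| LTS11210 week | Weeks since EFC11072 baseline | Share before entry |
|---|---|---|
| 48 | 100 | 52% |
| 96 | 148 | 35% |
| 144 | 196 | 27% |
| 192 | 244 | 21% |

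These are shares of time, not of damage.

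**2. What a cumulative progression rate implies.** Let I be the rate from the EFC11072 baseline and p the proportion already progressed at entry, and suppose scores do not fall. Progression within LTS11210 then lies between I − p and I. If progression in the two periods is independent, it equals 1 − (1 − I)/(1 − p). With an assumed I = 60%:

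- p = 60%: 1 − 0.40/0.40 = 0%
- p = 40%: 1 − 0.40/0.60 = 33%
- p = 30%: 1 − 0.40/0.70 = 43% (bounds 30% to 60%)

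The reported 60% cannot distinguish these cases.

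**3. What the means add.** Take two assumed courses with the same Week 48 results: 60% progressed and mean change 3.0.

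- Course A: all progression before entry. Rate 60% at entry, 0% afterwards; mean 3.0, then 0.0.
- Course B: equal, independent periods. Each has 37% progressing, since 1 − 0.6325² = 0.60; mean 1.5, then 1.5.

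The mean change at Week 0 (3.0 against 1.5) separates them, provided it is tabulated for the same patients. So the continuous results are informative, but the difference between two marginal means carries no within-patient confidence interval. Comparing entry with any visit after Week 48 also crosses reading sessions.

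**4. What the listed films allow.** Same-campaign pairs are EFC11072 EOT to Week 48 (Campaign 1), Week 48 to 96 (Campaign 2), and Week 96 to 144 and 144 to 192 (Campaign 3). Together they cover entry to Week 192 without a gap. Appendix D yields a total change score per time point, so an interval change is the difference between two such scores.

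**5. Why extrapolated scores must be left out.** By SAP 2.1.4 H, with b the daily slope from Week 96 to the last measurement, Week 144 = S96 + 336b and Week 192 = S96 + 672b. If both are imputed from that slope, the change from 96 to 144 is 336b and from 144 to 192 is 672b − 336b = 336b. The two intervals are identical by construction.

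**6. Illustration for former placebo patients.** The share of damage before entry is y/(y + r·w/52), with an assumed y of 2 to 3 units in the parent year and r of 0.3 to 1.0 unit per year afterwards.

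- w = 48: 2/2.92 = 68% to 3/3.28 = 92%
- w = 192: 2/5.69 = 35% to 3/4.11 = 73%

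**The case against.** Cumulative reporting is a deliberate choice. Protocol 13.7 defines the outputs as two-, three- and five-year data, each including the EFC11072 baseline film. For patients on sarilumab throughout, that is a fair description of long-term structural outcome. The endpoint is secondary and descriptive, Protocol 13.5.5 permits sensitivity analyses, and SAP 2.4.5 defers further analyses to an integrated summary of efficacy. All of this stands, and it is why the cumulative tables should stay. But neither provision commits to an interval analysis.

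Three stronger readings are tempting and are not supported:

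- **That the plan cannot show maintenance at all.** Actual scores and mean changes by visit and previous treatment give informal information on change within the extension. The firm limitation is in the binary rate.
- **That all former placebo patients spent a full year on placebo before entry.** Rescue from Week 16 rules this out for some. SAP section 3 itself names rescue as a complication of analysis by previous treatment.
- **That every campaign can give progression since entry.** Only Campaign 1 lists the entry film, and that film may be a last available one from before EOT. Campaigns 2 and 3 support intervals only.

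**Conclusion.** The point holds in a limited form. The progression rate at Weeks 48 to 192 cannot separate damage before entry from progression during LTS11210, and the visit means fill the gap only informally. The pre-entry share of the time window, 52% at Week 48 falling to 21% at Week 192, follows directly from the documents. The 60% example rests on assumed rates, non-falling scores and, for its point values, independence. The 68–92% and 35–73% shares likewise come from assumed progression rates and should not be read as estimates for this trial.

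Because the endpoint is descriptive, no formal conclusion is invalidated. The addition is still worth making, since it lets the endpoint address its stated purpose. A reader might infer that interval results would prove a maintained drug effect. They would not: with no control arm they describe progression on treatment, not a comparative effect.

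**What to change.** Keep the cumulative tables. In SAP 2.1.4 H and I, 2.4.5 and Appendix B, add descriptive within-patient results by previous treatment: mean change with 95% CI, and the percentage with change above zero. Use reads from one campaign only for each interval:

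- EFC11072 EOT to Week 48 (Campaign 1)
- Week 48 to 96 (Campaign 2)
- Week 96 to 144, and Week 144 to 192 (Campaign 3)

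State these rules:

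- Include patients with observed scores at both ends of the interval, and exclude linearly extrapolated scores.
- Do not count missing as progression; report the number missing for each interval.
- Flag former placebo patients who received rescue in EFC11072.
- Flag Campaign 1 intervals that start from a last available film earlier than EOT.

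The cost is SAP wording, a few tables and a smaller observed-case denominator; no new films or reads are needed. Same-session change from entry to Week 96 or Week 192 would remain unavailable unless the EFC11072 EOT film were added to Campaigns 2 and 3.
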